3.1.1 Dose Interruption and Reduction

Adverse Events:

It is recognized that some AEs may require dose adjustment or study drug discontinuation. Guidelines for dose reduction are outlined in Table 3-1.

Table 3-1 Guidelines for Dose Interruption and Reduction^a

AE	Occurrence ^b	Action
ALT or AST elevations (range 3 to 5 \times ULN) or ALP $>3 \times$ ULN and $>2 \times$ baseline	First	
 • If asymptomatic (no nausea, anorexia, vomiting), repeat test within 72 hours^c and, if stable or lower, may continue dosing of study drug. • If on repeat test value has increased further but remains $<5 \times$ ULN and asymptomatic, withhold study drug and retest weekly until values becomes stable. When stabilized to $<5 \times$ ULN, continue dosing with the study drug. • If symptomatic or $>5 \times$ ULN, withhold csDMARDs and study drug. Follow the subject weekly until symptoms abate and values return to baseline per confirmation from central laboratory, at which time csDMARDs may be restarted at the prior dose and study drug may be restarted at a reduced dose by skipping one of the doses. 
Note: Discontinue study drug permanently if the ALT elevation is accompanied by an elevation in direct bilirubin to >2 mg/dL (34.2 mmol/L).

	Second	Discontinue study drug permanently.
ANC $<1500/\text{mm}^3$ or $<1.50 \times 10^9/\text{L}$	First	Study drug must be withheld. Repeat the test weekly until value return to baseline or $\geq 1500/\text{mm}^3$ or $\geq 1.5 \times 10^9/\text{L}$, and then restart at a reduced dose by skipping one of the doses.
	Second	Discontinue study drug permanently if the intolerance reoccurs or persists.
Sustained increased systolic (>170 mm Hg) or sustained increased diastolic (>100 mm Hg) blood pressure in a previously normotensive subject	First	
Study drug may be withheld and then restarted at a reduced dose by skipping one of the doses.
 
Irrespective of study drug dose adjustment, subjects who develop a sustained increased systolic (>140 mm Hg) or a sustained increased diastolic (>90 mm Hg) blood pressure should be started on antihypertensive medications (ie, diuretics, calcium channel blockers, ACE inhibitors, etc.) or have their antihypertensive regimen adjusted if already on any antihypertensive agent.

	Second	Discontinue study drug permanently if the hypertension reoccurs or persists.

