Intolerable nausea or vomiting	First	Study drug may be withheld and then restarted at a reduced dose by skipping one of the doses.

AE	Occurrence ^b	Action
	Second	Discontinue study drug permanently if the intolerance reoccurs or persists.
QTcF >500 ms for female subject OR >480 ms for male subject, at any time point	-	
The ECG should be repeated as triplicate (all three within 2 minutes) and a cardiology consult may be obtained as medically necessary.
 
 • If the repeat ECG confirms QTcF >500 ms (females) or >480 ms (males), dosing must be interrupted for up to 14 days • If the QTcF resolves to ≤480 ms (males and females)/they may resume dosing at the reduced dose by skipping one of the doses (ie, morning or evening) • If the QTcF remains >480 ms (males and females) after 14 days of dose interruption, the study drug must be permanently discontinued.
QTcF change of >30 ms from baseline	-	If the QTcF has increased >30 ms when compared to the baseline with no other known etiology, and the PI considers it clinically significant then a confirmatory ECG (single) will be performed and dose should be reduced by skipping one of the doses (ie, morning or evening) for the remainder of the study.

Abbreviations: ACE, angiotensin-converting-enzyme; AE, adverse event; ALP, alkaline phosphatase; ALT, alanine aminotransferase; ANC, absolute neutrophil count; AST, aspartate aminotransferase; csDMARDs, conventional synthetic disease-modifying antirheumatic drugs; ECG, electrocardiogram; MOA, mechanism of action; PI, principal investigator; QTcF, QT interval correction for heart rate (QTc) using Fridericia's correction formula; ULN, upper limit of normal

- ^a These are examples based on previously observed AEs for agents with similar MOA (ie, fostamatinib). All other potential/spontaneous Grade 3/4 AEs that can warrant dose reduction or interruption are not excluded and will be assessed on an ongoing basis during the study. Those would be evaluated upon judgment by the principal Investigator and the safety operations team.
- ^b First/second occurrence relates to AE; abnormalities at repeat tests during monitoring of an AE are considered to belong to the same event (AE).
- c A central laboratory must be used for repeat ALT, AST, ALP or ANC.

Subject Error

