6.4.5.5 Reporting Serious Adverse Events

Any AE that meets SAE criteria (Section 6.4.5.2) must be reported to PPD Pharmacovigilance (PVG) immediately (ie, within 24 hours) after site personnel are aware of the event. This must be done via the eCRFs on the AE page. The entry will automatically be

sent to the PPD PVG team for review. If the eCRF system is unavailable, a manual SAE form may be used and faxed to the numbers outlined below.

The nonserious adverse event of special interest (AESI) defined in Section 6.4.5.6 should be recorded in the eCRF using the same process as for reporting SAEs.

The following contact information is to be used for PPD PVG:

PVG [contact]/[contact]

PVG Fax line: [contact]/[contact] or [contact]

6.4.5.6 Suspected Unexpected Serious Adverse Reactions and Nonserious Adverse Events of Special Interest

The following nonserious AESI should be recorded on the eCRF using the same process as for reporting SAEs.

- **Neutropenia** with fever defined as ANC <1500/mm³ or <1.5 × 10⁹/L on the most recent complete blood count with fever equal to or greater than 38°C that does not fulfill any of the serious criteria, ie, hospitalization.
- **Hepatotoxicity** defined as ALT >3 × ULN plus total bilirubin >2 × ULN that does not fulfill any of the serious criteria, ie, hospitalization. This information should be recorded on the drug induced liver injury eCRF each time the elevated laboratory parameters are met during the study.

Oscotec Inc. will promptly evaluate all suspected unexpected serious adverse reactions (SUSARs) and nonserious AEs of special interest against cumulative product experience to identify and expeditiously communicate possible new safety findings to Investigators, institutional review board (IRBs)/independent ethics committee (IECs), and applicable health authorities based on applicable legislation.

To determine reporting requirements for single AE cases, Oscotec Inc. will assess the expectedness of these events using the study drug Investigator's brochure. Reporting requirements will also be based on the Investigator's assessment of causality and seriousness, with allowance for upgrading by Oscotec Inc. as needed.

Osco Inc. will compare the severity of each SUSAR and the cumulative event frequency reported for the study with the severity and frequency reported in the applicable reference document.

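### Table 3-1 ties no dosing action to the protocol's own hepatotoxicity definition, so some first-occurrence subjects who meet it may continue or resume study drug

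*Protocol*

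**What the plan says.** Protocol 6.4.5.6 lists two nonserious adverse events of special interest. One is hepatotoxicity, "defined as ALT >3 × ULN plus total bilirubin >2 × ULN". The consequences given there concern reporting: "The following nonserious AESI should be recorded on the eCRF using the same process as for reporting SAEs". Section 6.4.5.5 sets that process at 24 hours. The event also goes on a liver-injury eCRF each time the thresholds are met, and the sponsor "will promptly evaluate all suspected unexpected serious adverse reactions (SUSARs) and nonserious AEs of special interest". No dosing action is attached.

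Dosing is handled in Protocol 3.1.1, Table 3-1. The liver row is entered on ALT, AST or ALP. At a first occurrence:

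- With no symptoms, the test is repeated within 72 hours and the subject, "if stable or lower, may continue dosing of study drug".
- If the repeat is higher but still below 5 × ULN and there are no symptoms, study drug is held with weekly retests. Once values stabilize below 5 × ULN the instruction is to "continue dosing with the study drug".
- With symptoms, or above 5 × ULN, the instruction is to "withhold csDMARDs and study drug" until symptoms abate and values return to baseline.
- A note covers bilirubin: "Discontinue study drug permanently if the ALT elevation is accompanied by an elevation in direct bilirubin to >2 mg/dL".

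A second occurrence means a permanent stop. Total bilirubin does not appear in the table.

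**The concern.** The protocol names a pair of laboratory findings as hepatotoxicity and treats them as urgent enough for the SAE reporting route. The dosing table for the same laboratory tests never refers to that pair. Its bilirubin rule uses a different analyte (direct, not total) and a different scale (a fixed 2 mg/dL, not a multiple of ULN). A subject can therefore be reported as hepatotoxic within 24 hours and remain on drug, under the table as written, while the sponsor evaluates the event.

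Liver enzyme change is a named potential risk (Protocol 1.5). The previous multiple-dose study lasted 7 days and did not include 400 mg BID (Protocol 1.3), whereas this trial doses for 12 weeks. What is at stake is the safety of individual subjects. The efficacy analysis is not in question.

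**Working it through.** **Step 1. Follow one subject through both rules.** Take a first occurrence with no symptoms and ALT 4 × ULN. Assume a bilirubin ULN of 1.2 mg/dL, total bilirubin 3.0 and direct 1.8 mg/dL.

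- 6.4.5.6: ALT 4 > 3, and total 3.0 > 2 × 1.2 = 2.4. The definition is met.
- Table 3-1 note: direct 1.8 ≤ 2. No permanent stop.
- Repeat stable or lower: dosing may continue. Repeat higher but below 5 × ULN: hold, then resume once stable.

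By contrast, at total 4.0 and direct 2.4 mg/dL the note applies and drug is stopped permanently.

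**Step 2. Look for a hold elsewhere.**

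- Table 3-1 footnote a concerns other Grade 3/4 events: "Those would be evaluated upon judgment by the principal Investigator and the safety operations team". Grading under 6.4.5.7 is functional, so a laboratory finding without symptoms would ordinarily not reach Grade 3.
- Section 4.2.1 permits withdrawal for clinically significant biochemical change. It is permissive and gives no liver threshold.
- Section 6.4.4 requires clinically significant changes to be followed until values return to the reference range or screening level, or until the investigator judges follow-up unnecessary. It also adopts the FDA liver-injury guidance as a guideline for assessing liver tests. It writes no hold into the protocol.
- Table 3-1 footnote c names ALT, AST, ALP and ANC for the central-laboratory repeat, not bilirubin.

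The other event in 6.4.5.6, neutropenia with fever, is treated differently. Its ANC threshold (below 1500/mm³) is the same as the ANC row of Table 3-1, where withholding is mandatory.

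**Step 3. Size of the uncovered range.** Let T be total bilirubin in mg/dL and f the direct fraction, so direct = f × T. The definition is met when T > 2 × ULN. The stop note is met when f × T > 2, that is, T > 2/f. The uncovered range is 2 × ULN < T ≤ 2/f, which exists only if f < 1/ULN: below 1.00 at ULN 1.0, 0.83 at ULN 1.2 and 0.67 at ULN 1.5.

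The documents give neither ULN nor f, so both are assumed. Each cell shows the uncovered T in mg/dL, with its width in brackets:

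| ULN | f = 0.5 | f = 0.6 | f = 0.7 | f = 0.8 |
|---|---|---|---|---|
| 1.0 | 2.0–4.0 (2.00) | 2.0–3.33 (1.33) | 2.0–2.86 (0.86) | 2.0–2.5 (0.50) |
| 1.2 | 2.4–4.0 (1.60) | 2.4–3.33 (0.93) | 2.4–2.86 (0.46) | 2.4–2.5 (0.10) |
| 1.5 | 3.0–4.0 (1.00) | 3.0–3.33 (0.33) | none | none |

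In the two empty cells the note triggers first, at 2.86 and 2.5 mg/dL. The cells show what is possible, not how likely it is.

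**The case against.** The strongest reply is that a reporting threshold and a dosing threshold need not coincide. Table 3-1 is headed as guidelines and its footnote calls the entries examples. Its wording for the stable subject is permissive, so nobody is told to keep dosing. A direct-bilirubin stop is a defensible choice, because a total-bilirubin rule will also catch benign elevations. The path needs five conditions at once, and the size rests on assumed values. The FDA guidance named in 6.4.4 may also bear on dosing; its content is not in the documents, so that cannot be settled here.

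Most of this stands, and it rules out stronger readings. A reader might infer that the protocol contradicts itself. It does not: the two sections serve different purposes. A reader might infer that nothing happens to this subject. That is also wrong: the repeat test, the hold if values rise, the 24-hour report and the sponsor evaluation all apply. Nor does the lack of a safety monitoring committee (Protocol 6.7) add much, since this is a decision about one subject and the sponsor already reviews each case.

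What the reply does not supply is a hold. Each safeguard either concerns reporting and assessment or leaves the dosing decision to judgment.

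**Conclusion.** The point holds as a cheap improvement. On a literal reading, a first-occurrence subject with no symptoms, ALT 3 to 5 × ULN, total bilirubin above 2 × ULN and direct bilirubin at or below 2 mg/dL meets the protocol's hepatotoxicity definition and may continue or resume dosing. That follows from the text alone. The width of the gap, from none to 2.0 mg/dL of total bilirubin, depends on the assumed ULN and direct fraction. Its frequency is unknown, so no claim is made that many subjects would be affected.

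**What to change.** Keep the permanent stop for direct bilirubin above 2 mg/dL and add one line to the liver row of Table 3-1:

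*If the hepatotoxicity definition in 6.4.5.6 is met, withhold study drug at once, include total and direct bilirubin in the repeat test, and restart only after the investigator and the medical monitor/safety operations team document another cause; csDMARD interruption is at the investigator's judgment.*

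The existing csDMARD hold for symptoms or values above 5 × ULN is unchanged. The new line should not replace the direct-bilirubin note. At an assumed ULN of 1.5 mg/dL and f = 0.8, the note acts above 2/0.8 = 2.5 mg/dL total and the definition only above 2 × 1.5 = 3.0, so replacing the note would lose the stop between 2.5 and 3.0. A compulsory csDMARD hold is not advised for this added group, because 5.8.1 keeps background therapy stable and interrupting it could affect DAS28.

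The cost is small. Both bilirubin fractions are already in the chemistry panel (6.4.4), and the sponsor already evaluates each event (6.4.5.6). The downside is a few more study-drug interruptions, some for benign bilirubin elevation, since inclusion criterion 6d admits total bilirubin just under 2 × ULN.

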- To investigate the pharmacokinetic (PK) profile of SKI-O-592 (the free base of SKI-O-703) and its metabolites (M2 and M4)
- To evaluate the effects of SKI-O-703 on exploratory pharmacodynamic (PD) biomarkers

Exploratory Objectives

- To evaluate the PK/PD relationship between plasma concentrations of SKI-O-592, M2, and M4 and the percent change in activated gp53/CD63+ basophils in peripheral blood

Subject Population

Inclusion Criteria

Each subject must meet all the following criteria to be enrolled in this study:

1. Subject is an adult male or female aged ≥ 18 years old at time of signing the informed consent (or per local customs for ≥ 19 years of age for Korean subjects).
2. Subject with Body Mass Index (BMI) of ≥ 18 and < 40 kg/m 2 at screening.
3. Subject who has a diagnosis of RA according to the 1987

American College of Rheumatology (ACR) criteria or the 2010 ACR/European League Against Rheumatism classification criteria for at least 6 months prior to Day 1.

4. Subject who has active disease at screening and baseline following treatment of RA with inadequate response to csDMARDs or anti-TNF α biological agent(s) as per 2012 update of the 2008 ACR RA treatment recommendations.
 - a. Active disease defined as:
 - presence of ≥ 5 swollen joints (of 28 assessed) and presence of ≥ 5 tender joints (of 28 assessed), and
 - serum high sensitivity C-reactive protein (hsCRP) concentration ≥ 0.6 mg/dL (or ≥ 6.0 mg/L; 1 mg/L = 9.524 nmol/L) at screening (based on the upper limit of normal [ULN] of laboratory normal range). Repeat may be allowed once during screening period (after an approval from medical monitor), if the result is considered unexplained/unexpected (eg, not corresponding with clinical disease activity or discordant with recent local result).
 - b. At least ONE of the following treatments for RA must have been received:
 - anti-TNF α biological agent(s): Includes at least 1 of the following treatments, with completed washout period indicated prior to Day 1 dosing

adalimumab (Humira $^{\circledR}$)	60 days washout
etanercept (Enbrel $^{\circledR}$)	30 days washout
infliximab (Remicade $^{\circledR}$)	60 days washout
certolizumab pegol (Cinzia $^{\circledR}$)	60 days washout
golimumab (Simponi $^{\circledR}$)	60 days washout
 - csDMARD therapy: Includes at least 1 of the following dosing regimen for at least 90 days of continuous use (prior to Day 1 dosing)*:

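### The SI value in the direct-bilirubin stopping threshold has the wrong unit prefix: 2 mg/dL is 34.2 µmol/L, not 34.2 mmol/L

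*Protocol*

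**What the plan says.** Table 3-1 in Protocol Section 3.1.1 sets out dose interruption and reduction. Its first row covers ALT or AST between 3 and 5 times ULN, or raised ALP. A note under the first occurrence gives the action, "Discontinue study drug permanently if the ALT elevation is accompanied by", and then the threshold, "elevation in direct bilirubin to >2 mg/dL (34.2 mmol/L" (the bracket closes after the unit). The threshold is thus stated twice, in mg/dL and in an SI unit.

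No other bilirubin limit in the protocol carries a concentration that could confirm or correct this one. Inclusion criterion 6 (Section 4.1.1) limits total bilirubin as a multiple of ULN. The hepatotoxicity event of special interest (Section 6.4.5.6) is defined as raised ALT "plus total bilirubin >2 × ULN that does not fulfill any of the serious criteria". The SAP gives no bilirubin threshold in either unit.

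**The concern.** A threshold given in two units has to describe one concentration. Here the mg/dL value is a plausible clinical limit, while the bracketed value, taken as printed, could never be reached. A stopping rule applied from the bracket alone would never trigger.

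The number decides whether a patient stops drug for good. Section 1.5 names liver enzyme changes as a potential risk, and Section 1.3 states that 400 mg BID has not been given to humans before. Sections 6.7 and 11.1.1 provide for neither a safety monitoring committee nor an external data monitoring committee, so the written rule carries more weight at the site. The trial recruits in the United States, Europe and South Korea (Section 4.1), so some sites may well read their results in SI units.

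The central laboratory does not fully close the route. Section 6.4.4 allows local results to support adverse event assessment, and footnote c of Table 3-1 requires the central laboratory only for repeat ALT, AST, ALP or ANC, not for bilirubin.

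**Working it through.** **Inputs**
- Threshold in conventional units: 2 mg/dL (Protocol Table 3-1).
- Printed SI equivalent: 34.2 mmol/L (same place).
- Molar mass of bilirubin: not in the documents. Assumed to be 584.66 g/mol for unconjugated bilirubin (checked over 584 to 585). As a wider range, conjugated forms are assumed to be 760.8 and 936.9 g/mol.

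**Step 1: check without any assumed molar mass.** 2 mg/dL × 10 dL/L = 20 mg/L. Molar mass implied by a pair = mass concentration / molar concentration.
- As printed: 20 mg/L / 34.2 mmol/L = 0.585 mg/mmol = 0.585 g/mol. Hydrogen is about 1 g/mol, so the pair is impossible for any substance.
- With µmol/L: 20 mg/L / 0.0342 mmol/L = 584.8 g/mol.

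**Step 2: try to reproduce the printed figure.** Molar concentration = 20 mg/L / molar mass.

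| Assumed molar mass (g/mol) | 2 mg/dL in mmol/L | 2 mg/dL in µmol/L |
|---|---|---|
| 584 | 0.0342 | 34.25 |
| 584.66 | 0.0342 | 34.21 |
| 585 | 0.0342 | 34.19 |
| 760.8 | 0.0263 | 26.3 |
| 936.9 | 0.0213 | 21.3 |

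The digits 34.2 come out with the unconjugated mass and the unit µmol/L. No row gives anything near 34.2 mmol/L.

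**Step 3: size of the discrepancy.** Mass concentration in mg/dL = mmol/L × molar mass / 10.
- 34.2 × 584.66 / 10 = 2000 mg/dL, which is 1000 times 2 mg/dL.
- 34.2 × 760.8 / 10 = 2602 mg/dL, or 1301 times.
- 34.2 × 936.9 / 10 = 3204 mg/dL, or 1602 times.

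**Step 4: is this a convention of the document?** The protocol's other molar conversions do not share the problem. For hsCRP, inclusion criterion 4 gives "1 mg/L = 9.524 nmol/L", which implies 10⁻³ g/L / 9.524 × 10⁻⁹ mol/L = about 105,000 g/mol, plausible for a protein. For haemoglobin, inclusion criterion 7 gives 85 g/L or 5.28 mmol/L, which implies about 16,100 g/mol, again in a protein's range. The fault is confined to the bilirubin bracket.

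**The case against.** There are three serious objections.

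**It may be a reading error.** The whole discrepancy is one character, µ against m, in text extracted from a PDF by a program. The micro sign does survive in the cell-count units of inclusion criterion 7, but that is list text and this is a table cell. Other Greek letters survive in the Synopsis table. An artefact is therefore possible but not shown, which is why the fix starts with the original page.

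**Harm is hard to construct.** The mg/dL limit comes first and is unambiguous. A result of 34.2 mmol/L is not physiologically attainable, so a clinician would see the slip, and a site comparing a µmol/L result with 34.2 would decide correctly. The rule fails only if the prefix is copied literally, for instance into an alert or worksheet, and neither document mentions one. Table 3-1 is also headed as guidelines, and footnote a calls its entries examples. Other safeguards do not use the bracket: withholding when symptomatic or above 5 times ULN and stopping at a second occurrence (Table 3-1), withdrawal for clinically significant biochemical change (Section 4.2.1), the drug-induced liver injury guidance (Section 6.4.4) and special-interest reporting (Section 6.4.5.6). All of this stands and keeps the point minor. It does not remove it: special-interest reporting uses total bilirubin and triggers a report rather than a stop, and none of the others repeats the first-occurrence stop on direct bilirubin.

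**The replacement value depends on a molar mass.** Direct bilirubin is the conjugated fraction, and conjugated masses would give 21.3 to 26.3 µmol/L. But the printed digits match the unconjugated mass, so 34.2 µmol/L is evidently what was meant, and the prefix is wrong whichever mass is used.

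**Conclusion.** The concern holds: as supplied, the bracketed unit is wrong. That 34.2 mmol/L cannot equal 2 mg/dL needs no outside figure, because the pair implies an impossible molar mass. That the intended value is 34.2 µmol/L rests on an assumed molar mass of about 585 g/mol, with which the printed digits agree. On that mass the bracket overstates the threshold 1000-fold; on the conjugated masses the factor is 1301 to 1602.

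Severity is minor. The governing mg/dL value is correct, several independent liver safeguards remain, and nothing in the endpoints, analysis sets, power or SAP depends on this figure. Confidence is medium, solely because a misread character in the PDF has not been ruled out.

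**What to change.** Look at Table 3-1 in the original PDF. If the page reads µmol/L, nothing needs changing. If it reads mmol/L, replace 34.2 mmol/L with 34.2 µmol/L and leave the 2 mg/dL limit as it is. Then confirm that any laboratory alerts or site worksheets built from the table did not carry over the mmol/L figure.

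The cost is one character in one table cell plus that check. The SAP needs no change.

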5. Subject who has any condition that could confound the evaluation of the data or the effect of the study drug, such as:

- a. Any other inflammatory or rheumatic diseases, including but not limited to psoriatic arthritis, ankylosing spondylitis, spondyloarthritis, systemic lupus erythematosus, Lyme disease, or uncontrolled fibromyalgia. Subjects with inactive or well-controlled fibromyalgia will be allowed to be enrolled in this study if the disease does not impact the study assessments, as per the investigator's judgement. Subjects with Sjogren's disease secondary to RA are eligible.
- b. Any conditions significantly affecting the nervous system (ie, neuropathic conditions or nervous system damage) if it may interfere with the investigator's assessment on DAS including joint counts.
- c. Severe physical incapacitation (unable to perform routine self-care, has RA ACR functional status class 4 [Arnett et al 1988], or who cannot benefit from medication).
- d. Any other serious acute or chronic medical or psychiatric condition that may increase the risk associated with study participation or study drug administration or that may interfere with the interpretation of study.

6. Subject who currently has one or more of the following medical conditions which in the opinion of the investigator would put the subject at risk by participating in the protocol:

- a. Uncontrolled diabetes mellitus, even after insulin treatment.
- b. Uncontrolled hypertension (as defined by systolic blood pressure ≥ 160 mm Hg or diastolic blood pressure ≥ 100 mm Hg on >1 occurrence or as judged by the investigator).
- c. Clinically significant finding meeting any protocol exclusion criteria on chest x-ray. Chest x-ray must be obtained during the screening period, unless a radiograph lung imaging (ultrasound not acceptable) was obtained within 12 weeks prior to the screening visit.
- d. Evidence of cardiac conditions as defined by the following:
 - New York Heart Association (NYHA) class III or IV heart failure, severe uncontrolled cardiac disease (unstable angina), or myocardial infarction within the 6 months prior to Day 1.

- Clinically relevant or significant ECG abnormalities, including ECG and QT interval correction for heart rate (QTc) using Fridericia's correction formula (QTcF). Subject with prolonged QT interval (using QTcF) defined as QTc >450 ms for male and >470 ms for female at retest will be excluded at screening.

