6.4.2 Vital Sign Measurements, Height, and Weight

Vital sign measurements will include systolic and diastolic blood pressures, pulse rate, respiratory rate, and oral temperature (tympanic temperature for Korean subjects). The subject must be seated for at least 5 minutes before all measurements are taken.

Vital signs will be measured at screening and other visits as indicated in the schedule of events (Table 6-1).

Height will be measured at screening only. Weight will be measured at screening, Day 1 (Visit 1), and EOS (Visit 7).

When procedures overlap at the same timepoints, the vital parameters assessment will be performed first followed by laboratory parameters and other procedures.

The Investigator will determine whether any of the vital sign measurements are clinically significant or not clinically significant. Clinical significance is defined as any variation in results that has medical relevance and may result in an alteration in medical care (eg, active observation, diagnostic measures, or therapeutic measures).

If a clinically significant change from the screening value is noted, the clinically significant value and the reason for clinical significance will be documented on the AE page of the subject's eCRF. The Investigator will continue to monitor the subject with additional assessments until the value has reached either the reference range, the value at screening, or until the Investigator determines that follow-up is no longer medically necessary.

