6.4.5.2 Serious Adverse Events

An SAE is defined as any event that results in death, is immediately life-threatening, requires inpatient hospitalization or prolongation of existing hospitalization, results in persistent or significant disability/incapacity, or is a congenital anomaly/birth defect.

Important medical events that may not result in death, be life-threatening, or require hospitalization may be considered SAEs when, based upon appropriate medical judgment, they may jeopardize the subject or require medical or surgical intervention to prevent one of the outcomes listed in this definition. Examples of such medical events include an allergic bronchospasm requiring intensive treatment in an emergency room or at home, blood dyscrasias, convulsions that do not result in inpatient hospitalization, or the development of drug dependency or drug abuse.

Note: The AE terms neutropenia and hypertension should be used only when reporting events that meet the following criteria:

- The term neutropenia is reserved for reporting an absolute neutrophil count (ANC) $<1500/\text{mm}^3$ or $<1.5 \times 10^9/\text{L}$ and may or may not be associated with fever or concurrent infection.
- The term hypertension is reserved for reporting an increase in systolic blood pressure $>160 \text{ mm Hg}$, or diastolic blood pressure $>100 \text{ mm Hg}$, or any clinically significant increase in blood pressure that requires modification of the subject's antihypertensive regimen.

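### Table 3-1's only directed stop for raised blood pressure is limited to previously normotensive subjects, an undefined term, so some eligible subjects with hypertension have only discretionary routes to stopping

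*Protocol*

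**What the plan says.** Protocol 3.1.1, Table 3-1, gives guidelines for interrupting, reducing and stopping study drug. The blood-pressure row applies to sustained raised "blood pressure in a previously normotensive subject", with limits of systolic above 170 or diastolic above 100 mm Hg. At the first occurrence study drug may be withheld and restarted at a reduced dose. At the second the row reads: "Discontinue study drug permanently if the hypertension reoccurs or persists".

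The row also carries a treatment instruction with lower limits, which applies whether or not the dose is changed. It covers "subjects who develop a sustained increased systolic (>140 mm Hg", or diastolic above 90: these subjects should start antihypertensive treatment "or have their antihypertensive regimen adjusted if already on any antihypertensive agent".

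On entry, exclusion criterion 6b (Protocol 4.1.2) begins "Uncontrolled hypertension (as defined by systolic blood pressure". It sets limits of 160 systolic or 100 diastolic on more than one occurrence, or the investigator's judgment. Everything under criterion 6 concerns conditions "which in the opinion of the investigator would put the subject at risk by participating in the protocol".

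Three other provisions bear on the point:
- Section 6.4.2: "The Investigator will determine whether any of the vital sign measurements are clinically significant or not clinically significant". Significant changes are recorded as adverse events and followed.
- Section 6.4.5.2: "The term hypertension is reserved for reporting an increase in systolic blood pressure" above 160, diastolic above 100, or a significant rise that needs a change of antihypertensive regimen.
- SAP 9.4 uses 90 to 140 systolic and 60 to 90 diastolic as normal ranges for shift tables.

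Neither document says what previously normotensive means.

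**The concern.** Footnote a to Table 3-1 says that the rows reflect adverse events already seen with agents of similar mechanism, and Protocol 1.5 lists cardiovascular effects among the potential risks. The protocol therefore judged sustained raised pressure worth a directed stop. As worded, it withholds that stop from subjects who already have raised pressure. A known hypertensive with recurrent sustained pressure above 170 would be over the systolic level that defines uncontrolled hypertension at entry, yet would come under a weaker rule than a subject who entered with normal pressure. Because the term is undefined, two sites could treat the same subject differently.

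The signal so far is weak. In the multiple-dose study (Protocol 1.1) there were slight upward trends, with no significant change versus placebo. That study dosed healthy volunteers for 7 days at up to 200 mg BID (Protocol 1.3). This trial doses for 84 days and includes 400 mg BID, which Section 1.3 says had not been given to humans before.

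**Working it through.** No figure in the plan needs to be reproduced. The check compares provisions.

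**1. Is this the only directed stop triggered by pressure?** These are the provisions of both documents that could lead to a stop for raised pressure:
- Table 3-1, second occurrence: a directed stop, under the row's trigger and so under its restriction.
- Table 3-1, treatment instruction (>140/>90): directs antihypertensives, not a hold or stop.
- Footnote a: other Grade 3/4 events are left to the judgment of the principal investigator and the safety operations team. The grades in Section 6.4.5.7 do not settle the matter. Grade 2 involves no medical intervention, and Grade 3 requires prevented daily activity as well as intervention. Raised pressure that needs treatment but does not limit activity fits neither.
- Section 4.2.1, items 3 and 5: withdrawal for a serious or intolerable event, in the investigator's opinion and after conferring with the sponsor, or for a condition that justifies it. No pressure level is given.
- Section 6.4.2: record and monitor.
- Section 6.4.5.2: governs the reporting term only.

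So the second-occurrence line is the only directed one.

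**2. How does the row compare with the rest of the table?** There are 6 rows: ALT/AST/ALP, ANC, blood pressure, nausea or vomiting, QTcF level and QTcF change. Five direct permanent discontinuation at some point; QTcF change directs a dose reduction only. Of the 5, blood pressure is the only row that leaves a category of subject outside its trigger. The ALP limb also depends on baseline (above 2 times baseline), but as a threshold that any subject can cross. The QTcF level row sets different limits by sex but covers both sexes.

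**3. Who is left out?** It depends on what the undefined term means.
- *Natural reading: no pre-existing hypertension.* Subjects with treated and controlled hypertension, and known hypertensives below the 6b limits, are eligible but outside the row's study-drug actions.
- *Narrower gap: normal pressure before dosing, including on treatment.* Controlled subjects are covered. What remains is mainly entrants at about 140-159/90-99. The lower bound comes from the row's own >140/>90 treatment trigger and the SAP 9.4 ranges, the upper bound from exclusion 6b. The AE-term level (>160/>100) points the other way for this group, but it governs reporting and does not define normal pressure.

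**4. What is lost for one affected subject?** Dosing lasts 84 days, and vital signs are scheduled on Days 14, 28, 56 and 84.
- A rise at Day 14 that recurs or persists at Day 28: 84 - 28 = 56 days left; 56/84 = 67%.
- Recurrence or persistence at Day 56: 84 - 56 = 28 days left; 28/84 = 33%.

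These figures are illustrative. The trigger needs a sustained rise, which a single visit may not show. Footnote b assigns abnormal repeat tests during monitoring to the same event, so a second occurrence may be reached later, although the row's reference to persistence still reaches a continuing rise. Unscheduled visits could also shift the dates.

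**The case against.** The strongest reply is that the restriction may be deliberate. New sustained hypertension in a normotensive subject is more plausibly due to the drug. In a known hypertensive it may be background disease, for which adjusting the regimen is the sensible first step. Dropping the qualifier would direct stops for such fluctuation, in blinded placebo subjects too. The table is a set of guidelines, its entries are described as examples, and the row plainly foresees subjects already on antihypertensives.

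Part of this stands. The rule is guidance, attribution is harder in known hypertensives, and a reading that covers subjects controlled on treatment is possible. But the protocol gives no rationale for the limit, that reading leaves a residual group, and the missing definition lets sites differ. Nor does uncertain attribution argue well for continuing study drug through recurrent or persistent sustained pressure above 170/100.

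A reader might also infer more than the documents support:
- *That these subjects have no safeguard.* They have directed antihypertensive treatment, recording and monitoring under 6.4.2, and discretionary stopping under footnote a and 4.2.1.
- *That a required pause is lost.* The first-occurrence hold is optional for everyone.
- *That the absence of a safety monitoring committee (6.7) makes this much worse.* Individual stops rest with the investigator, who confers with the sponsor, so it adds little.

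**Conclusion.** The point holds at modest severity and is worth correcting. The only directed pressure-triggered stop is tied to an undefined subject category. On the natural reading it omits eligible subjects with pre-existing hypertension; if the term includes those normotensive on treatment, it omits mainly entrants at about 140-159/90-99. Which reading the authors intended cannot be settled from the documents.

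No number of affected subjects can be given. The documents report no baseline pressure distribution and no antihypertensive use, and only left-out subjects who then have sustained pressure above 170 or 100 are affected. The 56-day and 28-day figures describe one hypothetical subject and should not be read as a trial-level effect. It would also be wrong to conclude that this is the only row that takes baseline into account, since the ALP limb does so as a threshold.

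**What to change.** Delete the words that limit the blood-pressure row to previously normotensive subjects, so that it applies to anyone with sustained systolic above 170 or diastolic above 100 mm Hg. If the sponsor wants a separate policy for pre-existing hypertension, define previously normotensive and add a line for the other subjects with a rise-from-baseline criterion set by its clinical staff. The table already uses change from baseline for QTcF.

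The cost is one table row in a protocol amendment, with no new visits or procedures. There may be a few more interruptions or discontinuations. It should not be assumed that the analysis is untouched. Under SAP 4.2 the Visit 5 EOT assessment counts as Week 12 only for subjects who complete treatment, and the primary ANCOVA in SAP 8.2.1 uses observed cases. Each added early stop therefore removes that subject's Week 12 value from the primary analysis: one subject in a planned arm of 37 is 1/37 = 2.7%. The same value would be carried forward in the mITT analysis (SAP 8.2.2), and the subject would count as a non-responder in the mITT analysis of the DAS28 categories (SAP 8.4). The planned methods need no change, and this cost is small against the safety gain.
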